Stored electronic data that contains PHI and/or other types of identifiable data will be encrypted and password protected and stored on a secure server. Subject identifiers will not be reused or disclosed to any other person or entity for research unless required by law, for authorized conduct and oversight of the study, or for other IRB-approved research.

All protected health information will be kept in a secure location with limited access.

Following the completion of the analysis and the project, the key to the coding system will be destroyed by shredding the documents so that there is no direct or indirect link to subject identifiers and information.

13. Potential Benefits:

Potential benefits in determining whether the two neurosensory blockade techniques are different include identifying a potential difference in the area of sensory blockade of the thigh, a potential difference in strength as indicated by MVIC, as well as suggesting a potential improvement in analgesia of the thigh and subsequent increase in patient satisfaction, as well as decreased postoperative opioid usage for future patients.

Both neurosensory blockade techniques are very safe, have little or no pain associated with administration, and have the same cost.

14. Biostatistics:

Sample Size Estimation:

There is no prior study to provide basis for a sample size estimation. Thus the study is powered to achieve 70% power with two-sided alpha = 0.05 for testing the equivalence of the two blocking methods. With an equivalence margin of 2 points (two blocking methods will be equivalent if mean score for one blocking method within two points of the other) and assuming a standard deviation of 3 points, the study will have 70% power with n = 34 in each group (total n = 68).

Statistical analyses:

Data will be summarized as mean and standard deviation for continuous variables and frequency and percentages for categorical variables. The equivalence of the two blocking methods will be tested using the two-one-sided-tests (TOST) procedure following Schuirmann (1987).²⁸ Pain scores and opiate consumption will also be analyzed in subgroups according to the location and type of surgery (foot vs. ankle vs. leg) and presence of concurrent sciatic block.

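### Does calling the TOST level two-sided 0.05 leave the equivalence criterion open, or the trial short of its stated 70% power?

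*Combined protocol and SAP*

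**What the plan says.** Section 14 (Biostatistics), under Sample Size Estimation, sets the level and the target together: "the study is powered to achieve 70% power with two-sided alpha = 0.05 for testing the equivalence of the two blocking methods". The margin is 2 grid points, explained as "two blocking methods will be equivalent if mean score for one blocking method within two points of the other". The spread is set by "assuming a standard deviation of 3 points", and the result is that "the study will have 70% power with n = 34 in each group (total n = 68"). Under Statistical analyses the method is named: "The equivalence of the two blocking methods will be tested using the two-one-sided-tests (TOST) procedure", with a reference to the original TOST paper.

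Three things are not stated: the level of each one-sided test, the level of the confidence interval to be compared with the margin, and the true difference assumed for the power. No other section supplies them. The stopping paragraph at the end of section 14 speaks of significance and of overwhelming evidence but gives no level.

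**The concern.** TOST consists of two one-sided tests, each run at its own level. Run at 0.05 each, it is the same as asking whether a 90% confidence interval lies within the margin, and its overall size is 0.05. In most other settings two-sided 0.05 means 0.025 in each tail and a 95% interval. A literal reader could carry that meaning over and require a 95% interval inside -2 to +2.

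This is the only significance level in the plan, and it governs the only prespecified test of equivalence. The two readings give different verdicts for some results and different power at the same sample size. If the stricter one were applied, the trial would run well below a target that is already modest.

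**Working it through.** **Inputs, all from section 14 except the last.** Margin M = 2, SD = 3, n = 34 per group, power 70%, TOST. True difference δ = 0 is an assumption, because the plan states none. A single final analysis is taken first.

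**Standard error and degrees of freedom.** SE = 3 × √(2/34) = 0.728; df = 2 × 34 − 2 = 66. M/SE = 2/0.728 = 2.749.

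**Normal approximation.** Power = 2Φ(M/SE − z) − 1 at δ = 0.
- 0.05 per test: 2Φ(2.749 − 1.645) − 1 = 2 × 0.865 − 1 = 73.0%.
- 0.025 per test: 2Φ(2.749 − 1.960) − 1 = 2 × 0.785 − 1 = 57.0%.

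**Exact power** (t-based, integrated over the distribution of the pooled SD):

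| Calculation | Power at 34 per group | Smallest n per group for 70% |
|---|---|---|
| TOST, 0.05 per test (90% CI) | 71.8% | 34 (33 gives 69.9%) |
| TOST, 0.025 per test (95% CI) | 54.6% | 42 (41 gives 69.3%) |
| Two-sided 0.05 t-test for a 2-point difference | 77.3% | 29 (70.4%) |

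The plan's 34 per group is reproduced exactly by TOST at 0.05 per test, and by neither of the other two. A simulation of 400,000 trials gave 72.0% and 54.8% for the two TOST readings.

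**Size of the gap if the other reading were used.** 70.0 − 54.6 = 15.4 percentage points below the stated power.

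**False equivalence at a true difference of exactly 2, single look.** 5.0% at 0.05 per test and 2.5% at 0.025 per test. Neither exceeds 5%.

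**Where the verdicts would differ.** With an observed pooled SD of 3, the half-width is 1.668 × 0.728 = 1.21 for a 90% interval and 1.997 × 0.728 = 1.45 for a 95% interval. The largest observed difference that can be declared equivalent is 2 − 1.21 = 0.79 or 2 − 1.45 = 0.55. Only results between 0.55 and 0.79 depend on the reading.

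**Sensitivity to the assumed true difference.** At δ = 0.25 power is 69.1% (0.05 per test) or 52.1% (0.025 per test); at δ = 0.5 it is 61.4% or 45.2%. The match with 70% therefore rests on δ at or near 0.

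**The interim look.** Section 14 also plans an analysis at 34 patients (17 per group) and states no adjustment for it. Simulating looks at 17 and 34 per group, both at 0.05 per test with a true difference of 2, gives false equivalence of about 7.4% to 8.1%. The lower end is for TOST at both looks. The upper end is for one-sided non-inferiority at the interim, tested in the direction where the margin is breached. The 5.0% above is a single-look figure.

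**The case for a change.** The case for a change is that a criterion found only by working back from the sample size has not really been stated. The words on the page are two-sided 0.05, so an analyst who applied a 95% interval would have textual support, would work with about 55% power, and would reach a different verdict for an observed difference between 0.55 and 0.79. One phrase would settle this before any data are seen, and the sample size would not move.

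Some of this stands. The wording is loose, the per-test level is not written down, and the power figures are correct. But the 95% reading has to be brought in from outside: no section mentions such an interval or 0.025, and the reading contradicts the 70% given in the same sentence. The two-sided difference test is not a live alternative either, since the sentence is about equivalence. The adjective may simply refer to the margin applying in both directions. Given a named TOST procedure and a level of 0.05, 0.05 per test is the standard analysis, and it is the one that returns 34.

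Nor would a tidier sentence remove the risk of a false equivalence claim. That risk comes from the interim look, and wording that assumed a single final analysis would contradict the stopping rule in the same section.

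**Conclusion.** No change follows. The label is a clerical looseness. Margin 2, SD 3, 34 per group, 70% power and TOST fit together at 0.05 per one-sided test (71.8% against the stated 70%), so neither the sample size nor the power is wrong. The figure of about 55% arises only under a 95% interval that the plan never specifies. Writing the level down would record what analysts would already do.

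This rests on a true difference of 0, which the plan does not state, and on a single look for the 5% false-equivalence figure. With the planned interim look left unadjusted, that figure is about 7.4% to 8.1% at 0.05 per test. That is a question about the stopping rule, to be judged on its own, and rewording the alpha label would not resolve it.

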Eligible and interested females of childbearing age will have a urine pregnancy test the morning of surgery. Exceptions include surgically sterile women or women with medically confirmed menopause. Urine (5 ml) will be collected for the urine pregnancy test (UPT). This is the routine clinical practice at Clements University Hospital, Zale Lipshy Hospital and the Outpatient Surgical Center as a part of the pre-procedure standard of care. Any females with a positive UPT will be excluded from the study.

Following the discussion and UPT (if necessary), informed written consent for clinical care and participation in the study will be obtained.

Once a patient is enrolled, they will be randomized to one of two groups, mid-thigh ACB or distal ACB, using a computer generated randomization program. The site will be marked, and a time out will be performed. A grid will be marked starting with anatomical landmarks at the knee joint: the medial inter-knee-joint point where the tibia meets the femur, the mid medial patella, the mid lateral patella, and along the same line at the semitendinosus tendon and 5cm posterior from that point. Then 5cm intervals will be plotted progressing cephalad to a total of 15 centimeters. This will yield 20 grid points.

The distribution of baseline sensation will be evaluated at the grid and documented. The degree of sensory block will be evaluated over the grid area with Neuropen prick testing on a scale of 0-1, with 1 = normal sharp sensation, 0 = change of sensation. The Neuropen will be used for the standardization of force.¹⁹⁻²¹ The primary outcome will be the number of grid-points with a change in sensation at 20 minutes and 30 minutes after the block. The second post block measurement is to ensure that the block is effective, as this will vary with each patient, and there is potential to miss important sensory change if measurement is taken too early. The current clinical guidelines list a block onset time between 15-30 minutes.

MVIC of the ipsilateral quadriceps muscle will be assessed using a handheld dynamometer and recorded.²²⁻²⁵

Patients will receive a preoperative ultrasound-guided single-injection ACB at either the mid-thigh or distal approach according to their randomization and according to the technique descriptions provided in the Background section of this protocol and consistent with standard UTSW peripheral nerve block procedures.

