Billing should be in accordance with standard practice and not paid for by the study, as all procedures are deemed standard of care. Patients will not be reimbursed for participation of the research.

Recorded Measures:

1. Baseline number of grid-points with full sensation.
2. The number of grid-points with a change in sensation at 20-minutes after the block to determine distribution of cutaneous sensory blockade.
3. Baseline ipsilateral quadriceps MVIC: 3 measurements of 5 seconds each separated by 30 seconds while seated with hip and knee at 90 degrees
4. MVIC at 20 minutes and 30 minutes as tested with same method as baseline test
5. Block performance time (needle in skin until needle out of skin)
6. Patient satisfaction for postoperative pain management
7. Pain scores on a 0-10 Likert scale at PACU (1-h) and at postoperative Day 1 (POD1) approximately 24 h following to surgery (0=no pain, 10=worse imaginary pain)
8. For inpatients, all recorded pain scores in the first 24 hours
9. Opioid consumption in PACU and for first 24 h

PHI including name, date of birth, MRN number, contact information including phone number will be recorded. Demographic information such as age, height, weight, BMI, race/ethnicity, and gender will be recorded. Medical and surgical history including allergies, pre-existing condition such diabetes, and medication list, ASA classification, type of anesthesia, laboratory results, regional anesthesia techniques, sensory mapping for adductor canal block, postoperative pain management, postoperative pain scores, and type of surgery will also be recorded.

4. Study Procedures:

- Potential subjects will be identified at the orthopedic presurgical clinic, the anesthesia preoperative clinic or the Day Surgery Unit. The electronic medical record (Epic) will also be used for prescreening potential subjects.
- Recruitment and consenting at Anesthesia preoperative clinics, Day Surgery Unit.
- Randomization: A computer generated randomization list will be used for randomization list.
 - **Anatomical landmarks at the knee joint:**

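### The 24-hour opioid and postoperative pain comparisons do not adjust for preoperative opioid use, although users are eligible and the medication list is recorded; the cost is precision in secondary endpoints

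*Combined protocol and SAP*

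**What the plan says.** Section 14 (Statistical analyses) names two one-sided tests for the equivalence of the blocks. For these two outcomes it adds only this: "Pain scores and opiate consumption will also be analyzed in subgroups according to the location and type of surgery", plus subgroups by concurrent sciatic block. The endpoint list stratifies pain scores by type of surgery, and section 3 puts patients who have a sciatic block in a separate group for the pain analysis. No covariate is named for any outcome.

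On allocation, section 3 says that "they will be randomized to one of two groups, mid-thigh ACB or distal ACB, using a computer generated randomization program". Neither section 3 nor section 4 names a stratification factor.

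On eligibility, section 7 lists eight exclusions. The only one about a drug is allergy to amide local anesthetics; opioid use and chronic pain do not appear.

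On data, section 3 records "Medical and surgical history including allergies, pre-existing condition such diabetes, and medication list", and item 9 of its Recorded Measures is "Opioid consumption in PACU and for first 24 h". Baselines are recorded for grid-points and for muscle strength, but no pain score is scheduled before the block.

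The pain score is the outcome of Specific Aim 2. Opioid consumption is a separate item, secondary endpoint 3.

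**The concern.** Opioid use before surgery is a plausible predictor of opioid consumption and pain afterwards. If it does predict them, leaving it out of the analysis leaves explainable variation in the error term and widens the interval for the arm difference. That matters here because Hypothesis 2 is a claim of similarity, and such a claim is only as good as its interval is narrow. Lower opioid consumption is also one of the benefits the protocol hopes for in future patients. The information needed is already to be collected, so a none/any covariate would cost almost nothing.

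**Working it through.** **Inputs from the documents.** 34 patients per arm, 68 in total, with no stratification factor (sections 3 and 14). Section 14 states "70% power with two-sided alpha = 0.05 for testing the equivalence", "With an equivalence margin of 2 points" and "assuming a standard deviation of 3 points"; these refer to the grid-point score. No margin, SD or expected value is given for pain or opioid consumption.

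**Inputs that must be assumed.** The proportion p of prior users, and the user/non-user gap g in within-group SDs. These determine R², the share of outcome variance that prior use explains.

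**1. The plan's own figure.** SE = 3 × √(2/34) = 0.728, and 2/0.728 = 2.749. With each one-sided test at 0.05, power = 2Φ(2.749 − 1.645) − 1 = 2Φ(1.104) − 1 = 73.0%. The exact t-based calculation gives 71.8%, and 34 is the smallest group size that reaches 70%. The stated sample size is therefore reproduced. It belongs to the primary outcome and neither supports nor contradicts this point.

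**2. Gain from adjustment.** For a none/any covariate, R² = p(1 − p)g² / [1 + p(1 − p)g²], and the SE of the arm difference is multiplied by √(1 − R²).

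*Gap of 1 within-group SD (g = 1):*

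| Prior users | p(1 − p) | R² | √(1 − R²) | SE reduction |
|---|---|---|---|---|
| 10% | 0.09 | 0.09/1.09 = 0.083 | 0.958 | 4% |
| 20% | 0.16 | 0.16/1.16 = 0.138 | 0.928 | 7% |
| 30% | 0.21 | 0.21/1.21 = 0.174 | 0.909 | 9% |

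*Gap of about 2 SD.* Assume 20 mg (SD 15) in non-users and 60 mg (SD 30) in users, as oral morphine equivalents over 24 hours. Within-group variance is (1 − p) × 225 + p × 900; between-group variance is p(1 − p) × 40².

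| Prior users | Within | Between | Gap in SDs | R² | SE reduction |
|---|---|---|---|---|---|
| 10% | 292.5 | 144 | 40/17.1 = 2.3 | 144/436.5 = 0.33 | 18% |
| 20% | 360 | 256 | 40/19.0 = 2.1 | 256/616 = 0.42 | 24% |
| 30% | 427.5 | 336 | 40/20.7 = 1.9 | 336/763.5 = 0.44 | 25% |

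*Low end.* With 10% users and a gap of half an SD, R² = 0.0225/1.0225 = 0.022. At R² = 0.02, √0.98 = 0.990.

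The extra degree of freedom multiplies the SE by about √(64/63) = 1.008. That takes less than one percentage point off each reduction in the tables, and at R² = 0.02 it leaves a ratio of 0.998, practically no gain.

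**3. Chance imbalance.** In the second table, a one-SD imbalance in the proportion of users shifts the unadjusted difference by 40 × √(2p(1 − p)/34) = 2.9, 3.9 and 4.5 mg. The unadjusted SEs are √(436.5 × 2/34) = 5.1, √(616 × 2/34) = 6.0 and √(763.5 × 2/34) = 6.7 mg. The ratios, 0.57, 0.65 and 0.66 (from unrounded values), equal √R². The shift is thus already a component of the unadjusted SE and does not add to it.

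**4. Pain scores.** The milligram figures do not carry over to pain. In terms of R² alone, and after the degree of freedom, the SE ratio is 0.98, 0.96, 0.90 or 0.84 for R² = 0.05, 0.10, 0.20 or 0.30. The documents do not indicate which value applies.

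**The case against.** The strongest reply is that the plan contains no error here. The arms are randomized, so an unadjusted comparison is unbiased on average and keeps its error rate. The endpoints are secondary, and the protocol calls itself a pilot. The choice of one more prognostic covariate is a refinement. All of this stands, and it limits the point to efficiency.

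A reader might go further in four ways that the documents do not support:

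- **That opioid users bias the comparison.** With randomized arms and use that predates allocation, there is no systematic bias.
- **That exposure to chance imbalance is a second, separate defect.** Sizeable imbalances can occur: with 10, 20 or 30% users, the chance that the arms differ by at least 10 percentage points is about 15, 29 or 35%. But step 3 shows that this variation is already inside the unadjusted SE, so counting it again would state one loss twice.
- **That a reduction of 18 to 25% is to be expected, or that a few users dominate the variance.** Those figures need a gap of about 2 within-group SDs, for which the documents give no basis.
- **That Aim 2 loses this much.** The milligram figures concern opioid consumption, whereas Aim 2 concerns the pain score.

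It can also be said that section 14 gives no model or margin specific to pain or opioids, so the missing covariate is part of a wider gap. That is true, and the fix below fills part of it.

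**Conclusion.** The point holds as a modest improvement to the analysis of secondary endpoints. Opioid users are eligible, the data to identify them are to be recorded, and the plan makes no use of those data for the two outcomes where they are most likely to help. With 10 to 30% prior users, the SE of the opioid difference would fall by about 4 to 9% for a gap of 1 within-group SD and by about 18 to 25% for a gap of about 2 SD. If prior use explains only about 2% of the variance, there is practically nothing to gain. Prevalence and gap are both assumptions. The gain for pain scores cannot be sized from the documents. The validity of the randomized comparison, the primary grid-point analysis and the sample size are not in question.

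**What to change.** In section 14, prespecify a linear model for 24-hour opioid consumption and for the pain scores, with these terms:

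- arm;
- opioid use before randomization, none or any, taken from the medication list;
- type of surgery;
- concurrent sciatic block.

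Surgery and sciatic block belong in the model because the plan already treats them as important. Keep the separate pain analysis by sciatic block that section 3 promises, with the remaining terms applied within each group. State that the covariate is established use before randomization; the preoperative opiates that section 3 allows as part of usual care are a different thing and should not define it. Write this down before any outcome data are seen, since adjustment added after an imbalance has been noticed would look post hoc.

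The cost is wording in section 14 and one degree of freedom for the new term. Daily morphine equivalents should replace none/any only if the list records dose, which the protocol does not say. A single 0-10 pain score before the block would be a sensible covariate for pain, but it is new data collection (one question per patient) and is optional.
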